#### 4.1.2 Pre-clinical Trials

Immunogenicity as well as pre- and post-exposure prophylactic efficacy of VSV $\Delta$ GZEBOV-GP, has been demonstrated following a single IM injection in multiple nonclinical studies in rodent species and nonhuman primates (NHP). Briefly, vaccination of mice with a single intraperitoneal (IP) injection of as few as 200 plaque-forming units (pfu) of VSV $\Delta$ GZEBOV-GP provided 100% protection against lethal mouse-adapted ZEBOV challenge 28 days after immunization. Similarly, a single intramuscular (IM) vaccination of cynomolgus macaques with rVSV $\Delta$ G-ZEBOV-GP induced strong and long-lasting humoral and cellular immune responses and 100% protection against a lethal IM challenge of homologous ZEBOV given by the IM route 28 days later or by aerosol. Protection from aerosol challenge has not been replicated in more recent studies and vaccinated animals experienced pulmonary inflammation with significant lung pathology; the reasons for this are being studied further. Additionally, a single IM injection of rVSV $\Delta$ G-ZEBOV-GP protected macaques against lethal IM challenge with the West African EBOV-Makona strain, with complete protection achieved against challenge 7 days post vaccination and partial protection at 3 days post vaccination. In a post-exposure prophylaxis model, 50% of NHP vaccinated within 30 minutes after a severe (1000 median lethal dose [LD50]) aerosol EBOV challenge survived.

Various studies in animal models have shown no toxicities in rodent or NHP models, including in immunocompromised NHP; particularly noteworthy was the absence of neurovirulence in NHP following intrathalamic inoculation. Current Good Laboratory Practice (cGLP) repeated dose toxicology studies are ongoing to evaluate the toxicity and local tolerance of V920 in mice and monkeys. In these studies V920 was administered via IM injection on Study Days 1 and 14 followed by a 30-day observation period. BALB/c mice and cynomolgus monkeys received V920 at up to  $2.0 \times 10^7$  pfu/animal and  $1.0 \times 10^8$  pfu/animal, respectively. To date, there has been no evidence of systemic toxicity based on preliminary clinical pathology and necropsy data.

#### 4.1.3 Ongoing Clinical Trials

Eight Phase 1 and four Phase 2/3 clinical trials are ongoing. The Phase 1 studies have been undertaken in North America (U.S. and Canada), Europe (Switzerland and Germany), and non-epidemic regions of Africa (Gabon and Kenya) to evaluate the immunogenicity and safety of V920 administered as pre-exposure prophylaxis. The four late phase studies include (1) a Phase 2 placebo-controlled trial in Liberia, (2) a Phase 3 trial in Sierra Leone with early and delayed vaccination arms, (3) a Phase 3 ring vaccination trial in Guinea, and (4) a Phase 3 immunogenicity, safety, and consistency lots trial in North America and Europe. Robust antibody responses to the ZEBOV-GP (with 100% of subjects seroconverting by 28 days) have been noted both by the enzyme-linked immunosorbent assay (ELISA) and virus neutralization assays in the Phase 1 program. After qualification and validation, these assays will be used to assess the antibody responses from subjects in the Phase 2/3 studies. If one assay is found to be sufficient to characterize the immune response, use of the assay that does not add value may be discontinued.

Preliminary efficacy and effectiveness data have been assessed in an interim analysis of ring vaccination trial in Guinea. Per the publication, 7,651 subjects were included in the planned interim analysis which included 48 clusters (4,123 subjects) randomly assigned to immediate vaccination with V920 ( $2 \times 10^7$  pfu), and 42 clusters (3,528 subjects) randomly assigned to delayed vaccination with V920 ( $2 \times 10^7$  pfu). In the immediate vaccination group, there were no cases of EVD with symptom onset at least 10 days after randomization, whereas in the delayed vaccination group there were 16 cases of EVD from seven clusters reported, demonstrating a vaccine efficacy of 100% (95% CI: 74.7, 100.0; p=0.0036). At the cluster level, with the inclusion of all eligible adults, vaccine effectiveness was 75.1% (95% CI: 7.1, 94.2; p=0.1791). No new cases of EVD were diagnosed in vaccines from the immediate or delayed groups from 6 days post vaccination.

## 4.2 Rationale

### 4.2.1 Rationale for the Trial and Selected Subject Population

Future Ebola outbreaks are likely to occur in countries where HIV infection is endemic or present in large segments of the population. It is important to know whether V920 will be safe and effective in this patient population as efforts to roll out vaccination during an epidemic need to be quick and HIV testing may not be possible. Twenty two known HIV-infected individuals have received V920 in the Phase 2 placebo-controlled trial in Liberia, and the preliminary safety profile in this small number of subjects appeared to be generally similar to the overall vaccinated population. However, safety and immunogenicity of V920 has not been formally evaluated in HIV-infected individuals in a randomized controlled manner to date. This is what is intended with this study.

Persons 65 to 70 years were initially excluded and subsequently included as there are a number of potential participants in this age group who are interested in participating. The risk of including this age group is the risk that poor immunogenicity could be attributed to vaccine rather than to immunosenescence in this age group and that older HIV positive subjects may have a different safety profile. However, it is unlikely that immune and safety responses will be remarkably different in 60 to 65 year old subjects (who are currently eligible) compared to 66 to 70 year old subjects who will become eligible. To date over 400 non-HIV infected subjects over 65 years of age have been enrolled in clinical trials and safety concerns in this age group have not been identified to date. Detailed analyses of age strata  $>65$  years of age are ongoing.

### 4.2.2 Rationale for Dose Selection/Regimen/Modification

#### 4.2.2.1 Rationale for the Use of Placebo Control

The use of placebo control will allow for comparison of safety and immunogenicity against an inert substance (normal saline). It is ethical to use normal saline in this study as Ebola is not circulating in areas where the study will be conducted. If an Ebola outbreak were to occur and local public health authorities recommended Ebola vaccination then placebo participants could

choose to receive an Ebola vaccine. Local public health guidance in each study site would be followed.

#### **4.2.2.2 Vaccine Dose for This Trial**

One dose of  $\geq 2 \times 10^7$  pfu of the study vaccine or placebo will be administered at D0 in all Cohorts. In Cohort 5, a second dose of matching vaccine ( $\geq 2 \times 10^7$  pfu/ml) or placebo will be administered at Day 56. The rationale for assessing a second dose in HIV positive subjects is to access whether a second dose will provide a greater immune response or a response in a greater proportion of subjects in case one dose is less immunogenic in HIV positive subjects than in non-HIV positive subjects assessed in other studies. The 56 day interval is based on the interval utilized in other studies that include non-HIV positive adults and children.

#### **4.2.3 Rationale for Endpoints**

##### **4.2.3.1 Immunogenicity Endpoints**

1. Primary endpoints:
  - a. ZEBOV-specific antibody responses measured by ELISA and neutralization on Day 28 in Cohorts 1-5 combined.
  - b. ZEBOV-specific antibody responses measured by ELISA and neutralization on Day 28 after the last dose of vaccine (equivalent to Day 84 from first dose) in Cohort 5.
2. Secondary endpoints:
  - a. ZEBOV-specific antibody responses measured by ELISA and neutralization on Day 28 in Cohort 5.
  - b. ZEBOV-specific antibody responses measured by ELISA and neutralization on Days 180 and 365 after the first dose of vaccine.

The V920 vaccine candidate is a live recombinant vesicular stomatitis virus (VSV) expressing the glycoprotein (GP) of Zaire Ebola virus (ZEBOV). Two independent assays are currently being utilized in the clinical development program to clinically evaluate the immunogenicity of V920:

- GP-ELISA measures the total IgG antibody response and can also be correlated to the plaque reduction neutralization assay (PRNT) titer result.
- Plaque reduction neutralization assay (PRNT) is a functional assay and a gold standard platform in the field for quantitating the neutralizing antibody response elicited by the vaccine.

If in the clinical development program one assay is found to be sufficient to characterize the immune response, use of the assay that does not add value may be discontinued.

#### 4.2.3.2 Safety Endpoints

1. Primary endpoints:
  - a. The occurrence of adverse events, in all participants, in all cohorts:
    - i. The occurrence of each solicited local and systemic AE, during a 14-day follow-up period following each vaccination, and fever, arthritis, arthralgia, rash and blisters/vesicular lesions during a 42-day follow-up period following vaccination.
    - ii. The occurrence of any hematological (hemoglobin level, WBC, lymphocyte, neutrophil, eosinophil and platelet count) and biochemical (ALT, AST and creatinine) laboratory abnormality at days 0, 3, 7, 14, and 28 after each vaccination.
    - iii. The occurrence of any unsolicited AE, during a 42-day follow-up period after each vaccination.
  - b. The occurrence of vaccine related SAE through to Day 365.
2. Secondary endpoints:
  - a. Detection of rVSV by PCR in blood, urine, and saliva in all subjects (D3, 7, 14, 28, 42 following each vaccination)
  - b. Detection of rVSV by PCR in through 42 days from skin vesicles, joint fluid, or skin biopsies if specimens are obtained
  - c. The occurrence of any SAE through to Day 365
  - d. Decrease in CD4 T cell-count (i.e.,  $CD4 < 200 \text{ mm}^3$ )
  - e. Increase in HIV viral load (i.e.,  $VL > 50 \text{ c/ml}$  over two consecutive measurements)

Adverse events are collected 42 days post-vaccination for live-attenuated vaccines because of the time required for viral replication and manifestation of adverse events. The Memory Aid will prompt the subject to record his/her temperature for 42 days following vaccination starting with the day of vaccination (D0-D42). Injection site and systemic reactions will be monitored on the day of vaccination (D0) and for 14-days post-vaccination (D1-D14). In addition subjects will be prompted for joint pain, joint swelling, rashes, and blisters or vesicular lesions during the 42-day post-vaccination period as these events have been reported in the development program. Subjects who demonstrate these symptoms may be asked to return to the study site for additional evaluation and work-up. All other unsolicited systemic and/or injection-site adverse events will be recorded during the 42-day post-vaccination period. Following the 42-day detailed safety reporting period, any serious adverse events (SAEs) that occur through 12 months after first vaccination are to be reported in order to provide long-term safety data. Safety laboratory data is obtained through Day 42, as in Phase 1 studies transient decreases in white blood cells and platelets have been assessed for 28 days in HIV- subjects.

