#### 4.3.1.3 Reactions to V920

Detailed safety data collected in the Phase 2 and 3 studies to date have demonstrated V920 to be generally well-tolerated when administered to healthy, non-pregnant, adults. Injection site reactions following vaccination are generally mild to moderate and self-limited. Thereafter, there is a predictable period of early reactogenicity, including fever and a flu-like syndrome and resolves with 7 days. During this time, transient decreases in white blood cells and platelets

have also been observed but bleeding or increased risk of infection has not been reported. The early reactogenicity is likely to be a result of viremia with the vaccine virus which resolves within 2 weeks. Vaccine virus has been found in saliva, urine, and skin-vesicles in vaccines. Person-to-person transmission has not been documented, however transmission through shedding and close personal contact is accepted as a theoretical possibility. Joint pain (arthralgia) is part of the early flu-like syndrome in the first week after vaccination in up to 44% of vaccines. In a small proportion of subjects (<5%), joint swelling (arthritis) may develop in the 2nd to 3rd week after vaccination. The arthritis is thought to be virally-mediated, and while the majority of arthralgia and arthritis events resolved spontaneously, recurrent or persistent arthralgia and arthritis have also been reported. The safety profile reported from the Ebola-epidemic region has been similar to that observed outside the region.

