### 8.2.5.2 Statistical Methods for Safety Analyses

Safety parameters will be compared between V920 and placebo control. Fisher's exact or Chi-square test will be used to compare the frequency of local and systemic reactions between treatment groups as specified in the SAP.

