#### Vital signs & clinical laboratory measures

Mean values for each measure, including  $\pm$  one standard deviation, will be summarized for each treatment group. Shift tables may also be generated if a significant frequency of abnormalities is noted. Extreme values will be discussed individually.

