### 8.2.7 Sample Size and Power Calculations

For immunogenicity assessment, there is 80% power to detect a Geometric Mean Ratio (GMR) of 1.6 (V920 GP-ELISA GMT of 58 EU/mL vs. Placebo GP-ELISA GMT of 36 EU/mL, the lower limit of quantification [LLOQ]) and 90% power to detect a GMR of 1.7 (V920 GP-ELISA GMT of 62 EU/mL) if comparing all five cohorts (N=200 V920 vs. N=50 Placebo) combined. This power analysis assumes a 10% dropout, a standard deviation of 1 on the log scale, and a 2-sided 5%.

There is 80% power to detect a GMR of 2.9 (V920 GP-ELISA GMT of 105 EU/mL) and 90% power to detect a GMR of 3.4 (V920 GP-ELISA GMT of 124 EU/mL) if comparing each cohort independently (N=40 V920 vs. N=10 Placebo). This power analysis assumes a 10% dropout, a standard deviation of 1 on the log scale, and a 2-sided 5%.

For safety assessment, there is 80% power to detect a 12% difference in event rates that occur with a frequency of 1% in the control group if comparing four cohorts (N=200 V920 vs. N=50 Placebo) combined and a 46% difference if comparing each cohort independently (N=40 V920 vs. N=10 Placebo).

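### Laboratory safety is a primary yes/no endpoint, and the continuous values behind it get only raw group means: no change from baseline, V920-placebo difference or confidence interval is planned

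*Combined protocol and SAP*

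**What the plan says.** Section 4.2.3.2 makes laboratory safety a primary endpoint (1.a.ii), defined as "The occurrence of any hematological (hemoglobin level, WBC, lymphocyte, neutrophil, eosinophil and platelet count) and biochemical (ALT, AST and creatinine) laboratory abnormality". For every dose, the assessments run from the day of injection to Day 28, with visits on Days 3, 7 and 14 in between. The endpoint text gives no cut-off. Appendix 2 gives four ordered grades, described as guidelines that depend on institutional normal values.

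Section 8.2.5.2 opens with a general promise: "Safety parameters will be compared between V920 and placebo control". The only tests it names, Fisher's exact or chi-square, "will be used to compare the frequency of local and systemic reactions between treatment groups as specified in the SAP". For laboratory values, the subsection on vital signs and clinical laboratory measures says that means with "one standard deviation, will be summarized for each treatment group". It adds that "Shift tables may also be generated if a significant frequency of abnormalities is noted", and that extreme values will be discussed individually.

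The flow charts in section 6.0 schedule hematology and chemistry at screening, at Day 0 and at each visit through 42 days after vaccination. On the expected effect, section 4.3.1.3 describes the first week after V920: "During this time, transient decreases in white blood cells and platelets" have been observed. Section 4.2.3.2 refers to the same falls when it explains the laboratory follow-up. Section 8.2.7 states safety power only for event rates: "80% power to detect a 12% difference in event rates that occur with a frequency of 1% in the control group".

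**The concern.** Hemoglobin, white cells, lymphocytes, neutrophils, eosinophils, platelets, ALT, AST and creatinine are all continuous, and each subject has values from before and after vaccination. The effect already seen with V920 is a downward shift in two of them. A yes/no cut registers such a shift only through subjects who cross the threshold. If abnormalities are uncommon on placebo, most of the shift goes uncounted.

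The plan does keep the full scale, but only as a display. Raw means at each visit do not use each subject's own starting value, and no interval says how large a difference the data can rule out. So a primary safety endpoint has a general promise of comparison but no stated effect estimate.

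Section 4.2.1 says that safety has not been formally evaluated in HIV-infected people in a randomized, controlled way. With about 50 placebo subjects, a non-significant comparison of abnormality rates would leave open whether V920 lowers counts moderately in this population. The data that could answer this are already being collected.

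**Working it through.** **Inputs from the documents.** 200 V920 and 50 placebo subjects pooled, 40 and 10 per cohort; 1% control rate and a 12-point difference for safety (section 8.2.7). Two-sided 5% is stated for the immunogenicity hypotheses (8.2.5.1) and assumed here for safety. The 10% dropout is stated for immunogenicity only (8.2.7). Applied to safety as an assumption, it gives 0.9 × 200 = 180 and 0.9 × 50 = 45.

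**Assumed, because the documents do not give them.** One normally distributed measure at one visit, equal SDs, a pure shift in mean; placebo abnormality rates from 1% to 20%; a baseline correlation of 0.5; Fisher's exact test for abnormal against normal.

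**1. The plan's own safety power.** With p1 = 0.13 and p0 = 0.01, the pooled rate is (200 × 0.13 + 50 × 0.01)/250 = 0.106.
- Null SE = √[0.106 × 0.894 × (1/200 + 1/50)] = 0.0487.
- Alternative SE = √[0.13 × 0.87/200 + 0.01 × 0.99/50] = 0.0276.
- Power = Φ[(0.12 − 1.96 × 0.0487)/0.0276] = Φ(0.89) = 81%.

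This reproduces the stated 80% with no dropout. Exact Fisher power is 83% at 200:50 and 77% at 180:45.

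**2. What that difference means on the measurement scale.** For a normal measure, moving from 1% to 13% beyond a threshold is a shift of Φ⁻¹(0.13) − Φ⁻¹(0.01) = −1.126 + 2.326 = 1.20 SD.

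**3. A moderate shift, 0.5 SD, at 180:45, yes/no comparison.** The V920 abnormality rate is Φ[Φ⁻¹(p0) + 0.5]. Power is by full enumeration of Fisher's exact test.

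| Assumed placebo rate | Implied V920 rate | Fisher power |
|---|---|---|
| 1% | 3.4% | 0.1% |
| 2.5% | 7.2% | 10% |
| 5% | 12.6% | 22% |
| 10% | 21.7% | 40% |
| 20% | 36.6% | 54% |

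**4. The same shift on the full scale.** The noncentrality is shift/√(1/n1 + 1/n0), taken to a noncentral t.
- Unadjusted, 180:45: 0.5/√(1/180 + 1/45) = 0.5/0.1667 = 3.00, power 85%.
- Unadjusted, 200:50: 0.5/√(1/200 + 1/50) = 0.5/0.1581 = 3.16, power 88%.
- Baseline-adjusted, 180:45, correlation 0.5: the residual SD is √(1 − 0.25) = 0.866, the noncentrality 3.00/0.866 = 3.46, power 93%.

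**5. Sensitivity.**
- At a 0.75 SD shift and 180:45, Fisher power is 6% at a 1% placebo rate but 81% at 10%. Unadjusted means have 99%.
- Within one cohort (40:10) at 1.20 SD, Fisher power is 0.1% at a 1% placebo rate but 56%, 66% and 71% at 10%, 20% and 30%. Unadjusted means have 91%.

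The advantage of the full scale is present throughout. Its size depends heavily on the placebo abnormality rate.

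**The case against.** The strongest reply is that most of the information is not lost. Group means and SDs will be shown, and with the group sizes a reader can compute a difference and an interval. On that basis the pooled data have 85% power at 0.5 SD. This stands. A reader might infer that the two planned outputs together would probably miss a fall well under 1 SD, and the figures do not support that inference.

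Second, section 8.2.5.2 assigns Fisher or chi-square only to local and systemic reactions. For laboratory data the method is unspecified; the plan does not confine the comparison to the cut. This also stands, and it is why Fisher appears above only as an assumption.

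Third, the 1% is a generic planning rate. The endpoint covers any abnormality across nine measures and several visits, in subjects whom section 5.1.3 admits with out-of-range values judged not clinically significant. The placebo rate could be much higher. So the tempting conclusions that only very large shifts are detectable, or that single-cohort power is about zero, do not hold in general; the second is true only at a 1% placebo rate. The 10% dropout is likewise not stated for safety, and the safety population includes everyone who received a dose.

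Fourth, who crosses a clinical threshold is a proper safety question, and a mean can hide a few severe falls. Appendix 2 also has four grades, and grades hemoglobin on change from baseline. No primary hypothesis concerns laboratory values. These are good reasons to keep the occurrence endpoint. They do not explain why the continuous values carry no between-arm estimate.

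**Conclusion.** The concern holds as a gap in specification. A primary safety endpoint built on nine continuous measures has no planned change from baseline, V920-placebo difference or confidence interval, despite the promised comparison, the scheduled pre-vaccination samples and the white-cell and platelet falls already reported.

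For a 0.5 SD shift at 180:45, relying on the yes/no comparison gives between 0.1% and 54% power across placebo rates of 1% to 20%. Unadjusted means give 85% (88% at 200:50), and a baseline-adjusted comparison gives about 93%. These figures rest on a normal measure at one visit, Fisher's exact test, a two-sided 5% level, 10% dropout and a baseline correlation of 0.5. A composite over measures and visits would have different power. The pooled sizes apply to visits after the first dose; only Cohort 5 (40:10) has laboratory data after a second.

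The change is worth making, but the plan is not blind to such shifts: the means it already displays would carry much of the signal if a comparison of them were specified.

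**What to change.** In section 8.2.5.2, under vital signs and clinical laboratory measures, add the following for each measure named in endpoint 1.a.ii and each scheduled post-vaccination laboratory visit. Estimate the V920-placebo difference adjusted for the pre-vaccination value, with a 95% CI, by ANCOVA or a repeated-measures model with baseline as covariate. Log-transform skewed measures such as ALT, AST, white cells and eosinophils. State which sample (screening or Day 0) is the baseline. Present the results as estimation.

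Keep the occurrence endpoint and the graded abnormality counts as defined. The model is the between-arm analysis of the continuous values beside them; it does not replace endpoint 1.a.ii.

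The cost is SAP wording and a few more tables, with no new samples, visits or subjects. The downside is more unadjusted contrasts. Nine measures at the five visits after the first dose (Days 3, 7, 14, 28 and 42) make 45 intervals. With no true effect, about 45 × 0.05 = 2.25 would exclude zero by chance. Section 8.2.6 plans no multiplicity adjustment, so the text should say that single intervals are not to be read as tests.

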### 5.1.3 Subject Exclusion Criteria

Participants with any of the following criteria will be excluded:

1. History of prior infection with a filovirus or prior participation in a filovirus vaccine trial;
2. History of prior infection with VSV or receipt of a VSV-vectored vaccine;
3. Presence of any febrile illness or any known or suspected acute illness on the day of any first immunization (subject may be rescheduled);
4. Clinical manifestations of systemic diseases considered by the investigator to impact safety or immunogenicity
5. Receipt of systemic glucocorticoids (a dose  $\geq$  20 mg/day prednisone or equivalent) within one month, or any other cytotoxic or immunosuppressive drug within 12 months;
6. Receipt of any investigational drug within 12 months of vaccination;
7. Receipt of any live virus vaccine within 42 days prior to study entry or any other (non-live virus) vaccine within 14 days prior to study entry.
8. History of sensitivity to any component of study vaccines per investigator brochure or package insert;

**Any baseline laboratory screening tests which is outside of acceptable range as defined in the protocol (local site reference ranges): ALT, AST, creatinine, hemoglobin, platelet count, total white blood cell count, urine protein, urine occult blood, urine glucose AND considered clinically significant by the clinical investigator. The following five screening parameters have limits set:**

- a. absolute lymphocyte count  $\geq$ 1000 cells/mm^3
- b. hemoglobin not greater than 1.5 grams below the lower limit of the normal reference range at the local laboratory
- c. ALT, AST not greater than 2 to 2.5 times the upper limit at the local laboratory

- d. Platelet count  $\geq 125,000$  and  $\leq 550,000$
- 9. To exclude transient laboratory abnormalities, the investigator may repeat a specific test (E.g. hemoglobin) once during the screening period (I.e. a maximum of two tests), , and if the repeat test is normal, subject may be enrolled;
- 10. Have an active malignancy or history of metastatic or hematologic malignancy except non-melanoma skin cancers;
- 11. Suspected or known alcohol and/or illicit drug abuse within the past 5 years;
- 12. Moderate or severe illness and/or fever  $>101^{\circ}\text{F}$  ( $38.3^{\circ}\text{C}$ ) orally or  $> 100^{\circ}\text{F}$  ( $37.8^{\circ}\text{C}$ ) axillary within one week prior to vaccination;

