## 6.0 TRIAL FLOW CHART

### (COHORTS 1- TO 4)

Trial Period:	Screening	Vaccination	Follow-up							
			1	2	3	4	5	6	7	8
Visit Number/Title:	Screening		1	2	3	4	5	6	7	8
Day:	-30 to 0	0	3	7	14	28	42	180	365	
Scheduling Window (Days):	NA	NA	±1	±1	±3	±3	±7	±14	±28	
Administrative Procedures										
Informed Consent	x									
Inclusion/Exclusion Criteria	x	x								
Subject Identification Card	x	x								
Medical History	x	x								
Concomitant Medication Review	x	x	x	x	x	x	x	x	x	
Randomisation/Vaccine Administration		x								
Clinical Procedures/Assessments										
Full Physical Examination	x									
Height	x									
Weight	x									
Vital Signs (heart rate, blood pressure, respiratory rate, oral/tympanic/axillary temperature)	x	x	x	x	x	x	x	x	x	
Post vaccination Monitoring for Hypersensitivity Reactions (30 Minutes)		x								
Non-Serious Adverse Events Monitoring		x	x	x	x	x	x	x		
Serious Adverse Events Monitoring	x	x	x	x	x	x	x	x	x	

Trial Period:	Screening	Vaccination	Follow-up							
			1	2	3	4	5	6	7	8
Visit Number/Title:	Screening		1	2	3	4	5	6	7	8
Day:		-30 to 0	0	3	7	14	28	42	180	365
Scheduling Window (Days):	NA	NA	±1	±1	±3	±3	±7	±14	±28	
Distribute Patient Memory Aid and Review Procedures with Subject		X								
Review Arthralgia/Arthritis, Rash and/or Vesicular Lesion Reporting Requirements with Subject a	X	X	X	X	X	X	X			
Review Memory Aid with Subject			X	X	X	X	X			
Collect Memory Aid from Subject								X		
Laboratory Procedures/Assessments										
Hematology (~4mls)	X	X	X	X	X	X	X			
Urinalysis	X									
Chemistry (~8mls)	X	X	X	X	X	X	X			
Urine Pregnancy Test (if applicable based on subject's age/gender)	X	X								
HIV serology (if not previously documented) (~8mls)	X									
HBsAg (~8mls)	X									
Hepatitis B & C serology (combined with HBsAg)	X									
ZEBOV-specific Serum Antibodies (~20mls-combined with ZEBOV-specific Neutralizing antibodies)		X b				X		X	X	
ZEBOV-specific Neutralizing antibodies (see volume above)		X b				X		X	X	

Trial Period:	Screening	Vaccination	Follow-up							
			1	2	3	4	5	6	7	8
Visit Number/Title:	Screening		1	2	3	4	5	6	7	8
Day:	-30 to 0	0	3	7	14	28	42	180	365	
Scheduling Window (Days):	NA	NA	±1	±1	±3	±3	±7	±14	±28	
VSV (Blood, Urine and Saliva Sample) (~5mls blood)			x	x	x	x	x			
HIV viral load (~8mls)	x	x	x	x	x	x	x	x	x	
CD4/CD8 T Lymphocytes count (~4mls)	x	x	x	x	x	x	x	x	x	

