HIV RNA (reservoirs) (~20 mls combined with HIV DNA and HIV TILDA below)		x				x		x	x	
HIV DNA (reservoirs) (see volume above)		x				x		x	x	
HIV TILDA (reservoirs) (see volume above)		x				x		x	x	
*Biobank samples-optional (~35mls)		xb				x		x	x	
Total Blood volumes (*including optional Biobank sample)	~ 40mls	~64mls (*~89mls)	~29mls	~29mls	~29mls	~69mls (*~94mls)	~29mls	~52mls (*~87mls)	~52mls (*~87mls)	
a. Specimens should be obtained for rVSV detection by PCR in through 42 days from skin vesicles, joint fluid, or skin biopsies b. Specimens should be obtained before vaccination										

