Pre-existing conditions or signs and/or symptoms present in a participant prior to the first study injection are not considered to be adverse events. These events will be recorded in the participants' medical history.

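### Primary safety endpoint 1.a.ii has no new-or-worsened rule for laboratory abnormalities, leaves out the scheduled Day 42 tests, and has no count analysis in the SAP

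*Combined protocol and SAP*

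**What the plan says.** Section 4.2.3.2 places the laboratory endpoint, item 1.a.ii, under a parent line that reads "The occurrence of adverse events, in all participants, in all cohorts". The item covers haemoglobin, white cells, lymphocytes, neutrophils, eosinophils, platelets, ALT, AST and creatinine, and counts any "laboratory abnormality at days 0, 3, 7, 14, and 28 after each vaccination". It sets no baseline, grade or new-onset condition.

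The same section later states: "Safety laboratory data is obtained through Day 42". The Section 6.0 flow charts agree. In Cohorts 1 to 4, haematology and chemistry are marked at screening and on Days 0, 3, 7, 14, 28 and 42. In Cohort 5 they are also marked on Day 56 and on Days 3, 7, 14, 28 and 42 after dose 2. The footnote "Specimens should be obtained before vaccination" is attached to the antibody samples (and, in Cohorts 1 to 4, the biobank samples), not to haematology or chemistry.

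Section 5.1.3 excludes an out-of-range screening result only under a double condition; its list of tests ends "urine glucose AND considered clinically significant by the clinical investigator". Numeric limits are set for lymphocytes, haemoglobin, ALT/AST and platelets.

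Section 7.2 says that pre-existing conditions or "symptoms present in a participant prior to the first study injection are not considered to be adverse events".

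For laboratory measures, Section 8.2.5.2 plans means with one standard deviation by treatment group and individual discussion of extreme values. It adds: "Shift tables may also be generated if a significant frequency of abnormalities is noted". The only between-arm test that it names is for local and systemic reactions.

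**The concern.** An occurrence endpoint needs a rule that separates what followed the vaccine from what was already there. Item 1.a.ii has none and lists Day 0 among its event days. Under the literal wording, an abnormality present at vaccination is an event, and so is one that persists unchanged to Days 3 to 28. Deleting Day 0 alone would therefore not cure it.

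Background of this kind falls on both arms alike and makes them look more similar. That matters here because Sections 4.2.3.2 and 4.3.1.3 describe transient falls in white cells and platelets after this vaccine, and both analytes are in the endpoint.

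Two further gaps are independent of the dilution. Tests drawn on Day 42 fall outside the endpoint. And an endpoint defined per subject as an occurrence has no named analysis of counts; group means can conceal falls in individuals.

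**Working it through.** **1. Can a subject with a baseline abnormality enrol?** Compare the Section 5.1.3 limits with the Appendix 2 grades.

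| Analyte | Enrollable | Appendix 2, Grade 1 |
|---|---|---|
| Platelets | from 125,000 | 125,000 to 140,000 |
| ALT, AST | up to 2 to 2.5 x ULN | 1.1 to 2.5 x ULN |
| Lymphocytes | from 1,000 | 750 to 1,000 |
| Haemoglobin | up to 1.5 g below the local lower limit | out of local range by construction |

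The lymphocyte overlap is the single value 1,000. Total white cells and creatinine have no numeric limit. Neutrophils and eosinophils are in the endpoint but are not named as screening parameters. So mild baseline abnormality is possible in every analyte of the endpoint. How common it is cannot be read from the documents.

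**2. The plan's own safety figure.** Section 8.2.7 gives 80% power for a 12-point difference from a 1% control rate at 200 v 50. With a two-sided 5% level (stated for the hypotheses, assumed here for safety) and no dropout, 1% v 13% gives 81.3% by the pooled normal approximation and 83.2% by exact enumeration of Fisher's test. The figure reproduces.

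**3. Effect of counting baseline findings.** Let b be the share abnormal before vaccination, equal in both arms and independent of emergent events, and p the emergent rate. The observed rate is b + (1-b)p. The difference is then

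[b + (1-b)p1] - [b + (1-b)p0] = (1-b)(p1 - p0).

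Example, b = 0.05: placebo 0.05 + 0.95 x 0.01 = 0.0595; V920 0.05 + 0.95 x 0.13 = 0.1735; difference 0.114 = 0.95 x 0.12.

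Protocol scenario, 1% v 13%, 200:50, Fisher's exact test:

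| b (assumed) | Placebo | V920 | Difference | Power |
|---|---|---|---|---|
| 0 | 1.0% | 13.0% | 12.0 points | 83% |
| 5% | 6.0% | 17.4% | 11.4 points | 53% |
| 10% | 10.9% | 21.7% | 10.8 points | 39% |
| 20% | 20.8% | 30.4% | 9.6 points | 23% |

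Power falls much faster than the difference because the added background also raises the variance, most of all when the control rate starts at 1%.

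Alternative scenario with assumed emergent rates of 5% placebo and 20% V920:

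| b (assumed) | Placebo | V920 | Difference | Power |
|---|---|---|---|---|
| 0 | 5.0% | 20.0% | 15.0 points | 79% |
| 10% | 14.5% | 28.0% | 13.5 points | 48% |
| 15% | 19.3% | 32.0% | 12.75 points | 40% |
| 20% | 24.0% | 36.0% | 12.0 points | 34% |

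The result depends on the size of the true effect. At b = 15%, 30% v 5% emergent still has 82% power, and 40% v 5% has 98%.

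**4. Day 42.** No figure can be given, because the documents contain no Day 42 abnormality rate. The gap is simply that endpoint days stop at 28 while collection runs to 42.

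**5. Dose 2 in Cohort 5.** Day 0 after the second vaccination is study Day 56. An abnormality there may be long-standing or may follow dose 1. The Section 7.2 rule refers only to the first injection and does not settle it.

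**The case against.** A reader might infer that the plan definitely scores pre-existing abnormalities as events. The documents do not go that far. Item 1.a.ii is a sub-item of adverse events, and Section 7.2 takes findings present before the first injection out of that class. The listed days could also be meant as a visit-by-visit table with Day 0 as reference. This stands as a limit: the fault is a conflict with no rule for resolving it, not a settled decision to count baseline findings. Appendix 2 does grade change from baseline, but only for haemoglobin.

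A reader might also infer that Day 42 results are ignored, or that leaving them out causes the dilution. Neither holds. The samples are taken. Under Section 7.2 an abnormal laboratory finding can be an adverse event and is reportable through 42 days after each vaccination, so it then falls under primary endpoint 1.a.iii. Section 4.2.3.2 also notes that Phase 1 followed these falls for 28 days, which may explain the endpoint's last day. But 1.a.iii captures a Day 42 value only if an investigator reports it, which is not a systematic laboratory endpoint.

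Nor is it right that the SAP has nothing beyond means. Extreme values are discussed individually, safety parameters are to be compared between arms in general terms, and adverse events are tabulated. What remains is that no count-and-percent analysis of this endpoint is named and shift tables depend on an undefined frequency.

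Finally, the entry limits restrain baseline abnormality, and no test of laboratory abnormality is planned, so power has no exact counterpart in the SAP. Both points are fair and make the power figures illustrative.

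**Conclusion.** The concern holds in this form: primary endpoint 1.a.ii lacks a baseline or new-or-worsened rule although mild abnormality is enrollable, and its literal reading conflicts with Section 7.2. Under that reading the arm difference shrinks by (1-b), and the direction is not in doubt if baseline prevalence is similar in the two arms. The size is unknown because b is not given. The falls in power, from 83% to 53% or 39% in the protocol's scenario and from 79% to between 48% and 34% in the assumed one, rest on assumed prevalences, on independence of baseline and emergent findings and, in the second case, on assumed event rates. They do not show that a true effect would be missed; a large effect would survive.

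The omission of Day 42 and the missing count analysis are separate and follow from the text without assumptions. For a primary safety endpoint, this should be corrected.

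**What to change.** - **Endpoint (4.2.3.2, item 1.a.ii).** Define the event as a new or worsened-grade abnormality relative to the last value before that vaccination, on Days 3, 7, 14, 28 and 42 after each vaccination. Name the grading scale, and say which of the two haemoglobin scales in Appendix 2 applies. Reconcile the item with Section 7.2.
- **Timing (6.0).** State that haematology and chemistry samples on Day 0, and on Day 56 in Cohort 5, are drawn before dosing.
- **Dose 2.** Also show change from the value before dose 1, so that a Day 56 abnormality that followed dose 1 is not absorbed into the dose 2 baseline.
- **Analysis (8.2.5.2).** Report n (%) by arm with the difference and 95% CI, plus unconditional shift tables from pre-dose to worst post-dose grade. Keep the means as descriptive.

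The cost is endpoint and SAP wording, a flow-chart footnote and one programmed derivation. No sample or visit is added.
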